8. SF-12

**Month 3:** (titration down of the medication is not required)

1. In-person clinical visit is required for the final month 3 visit (no phone option).
2. Adverse events
3. Likert pain scale
4. NIH Pain Interference Scale
5. NIH Fatigue Interference Scale
6. NIH Sleep Disturbance Scale
7. Concomitant medication
8. Subjects can either can go off medication or be prescribed medication they were on (titration down is not necessary)

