## Pregabalin

**Pregabalin**, an analog of GABA, is an anticonvulsant that has been shown to have analgesic, anticonvulsant, and anxiolytic activity, although via GABA-independent mechanisms. Similar to gabapentin, it binds potently to the  $\alpha_2\delta$  subunit of voltage-activated calcium channels, reducing the release of several excitatory neurotransmitters. Unlike gabapentin, pregabalin exhibits linear pharmacokinetics across the standard dose range, and can be initiated at a therapeutic dose without a long titration. Pregabalin significantly reduced mean pain scores at a dose of 100 mg tid (3x/day) versus placebo in painful diabetic neuropathy. The target for improvement was a 50% reduction in pain. No titration was used, and significant pain relief was observed by the end of the first week. Secondary efficacy variables also improved significantly, including the SF-MPQ, sleep outcomes, pain domains in the SF-36, tension-anxiety, total mood scores, and both patient and clinician-rated global impressions. Other studies in diabetic neuropathy have demonstrated efficacy versus placebo using fixed or flexible dosing regimens ranging from 150 to 600 mg/day, whereas 75 mg daily in one study and 150 mg in another study did not differ from placebo. As a result, increasing the dose to 300 mg/day or higher in partial or non-responders who tolerate the medication seems appropriate.

The main adverse events of pregabalin were dizziness (up to 39%), somnolence (up to 22%), infection (15%), and peripheral edema (up to 17%), a profile similar to gabapentin. The frequency of side effects increases with higher doses. Adverse events were mostly mild to moderate in severity, and overall this drug is well tolerated. Infections were mainly of the upper respiratory variety. Eleven to 15 percent of pregabalin-treated patients discontinued taking it due to adverse events.

Pregabalin was released in the fall of 2005 with indications for both painful diabetic neuropathy and postherpetic neuralgia. It is a Schedule V medication in the US due to a low

frequency of euphoria, insomnia and headache with sudden discontinuation, and from responses on surveys of non-dependent sedative or hypnotic users.

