### **C. Study Design**

If a patient agrees to participate in the study, they will be randomized to one of the 4 drug options. They cannot be currently taking one of the study medications or similar class of medication and they must have a Likert type pain score of 4 or higher. They will then be written a prescription for the drug at the study dose. The drug is not provided by the study; the cost of the drug will be the responsibility of the patient or their insurance provider. Target drug daily doses are nortriptyline 75 mg; duloxetine 60 mg; pregabalin 300 mg; mexiletine 600 mg. Doses will be escalated weekly during the first month until the target doses are achieved (all by 4 weeks).

Doses will be escalated by the following schedule:

- Nortriptyline: 25 mg at bedtime for 1 week, then 50 mg at bedtime for 1 week, then 75 mg at bedtime
- Duloxetine: 20 mg for 1 week, then 40 mg for 1 week, then 60 mg daily
- Pregabalin: 100 mg at bedtime for 1 week, then 100 mg 2 times a day for 1 week, then 100 mg 3 times a day for the remainder of the study
- Mexiletine: 200 mg at bedtime for 1 week, then 200 mg 2 times a day for 1 week, then 200 mg 3 times a day for the remainder of the study

If suggested medications are not available in the dosage outlined in this protocol, then an alternate dosing schedule may be utilized providing that patients achieve the target daily drug dosage at week 3 of the study.

The length of the study for each patient is 3 months. After this point, they can stay on the medication of their choice.

If the patient cannot tolerate the maximum dose, then (at the discretion of the physician) they may be titrated down to the previously tolerable dose. Patients who are currently taking narcotics for pain control are eligible to participate in this study if they meet all other inclusion criteria.

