#### **a. Inclusion/Exclusion Criteria:**

Inclusion Criteria:

1. Age 30 or older.
2. Diagnosis of cryptogenic sensory polyneuropathy.
3. Likert Pain Score of greater than or equal to 4.
4. Must not currently be on nortriptyline, duloxetine, pregabalin or mexiletine or similar class of medication for at least 7 days from baseline study visit.

Exclusion Criteria:

1. Any medical condition or current medication (Appendix G) that would prevent them from taking either nortriptyline, duloxetine, pregabalin or mexiletine.

2. Unable to give consent.
3. Unable or not willing to comply with the study.
4. Other causes for polyneuropathy.

b. Study Procedures:

Prescreening: Subjects must be identified with having CSPN prior to the baseline visit into the study.

**Screening/Baseline Visit:** (Screening/baseline period may take up to 14 days if patients need to titrate down off of medication)

1. Subjects will be asked to read and sign the consent form.
2. Medical history
3. List of concomitant medication
4. Likert pain scale
5. NIH Pain Interference Scale
6. NIH Fatigue Interference Scale
7. NIH Sleep Disturbance Scale
8. A three month prescription will be given to the subject at this visit.

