9. SF-12
10. 28 day post call.
  1. There will be a call by the study coordinator to close out any adverse events left open at the end of the study.

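### At Month 3 sites are told for all four drugs that no taper is needed, although the protocol names pregabalin stopping effects, and the one later contact is stated only to close adverse events already open (minor)

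*Combined protocol and SAP*

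**What the plan says.** Three places in the combined protocol and SAP bear on the point.

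- **Exit instruction.** In section C, b. Study Procedures, the Month 3 heading states "titration down of the medication is not required". Item 8 of the same visit repeats it: "Subjects can either can go off medication or be prescribed medication they were on (titration down is not necessary". Neither line distinguishes between nortriptyline, duloxetine, pregabalin and mexiletine.
- **Pregabalin background.** Section B, Pregabalin, explains the drug's scheduling in a sentence that runs over a page break: "It is a Schedule V medication in the US due to a low" and then "frequency of euphoria, insomnia and headache with sudden discontinuation". It gives no rate, no severity and no advice on tapering.
- **Contact after Month 3.** The last item under Month 3 is a 28-day call: "There will be a call by the study coordinator to close out any adverse events left open at the end of the study". No other contact after Month 3 is scheduled.

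**The concern.** The protocol names a stopping effect for one of its own drugs, then gives a general exit instruction that does not mention it. A patient on the target dose who goes off pregabalin at Month 3 stops from 300 mg/day, and the text gives the site no prompt to offer a step-down.

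The second half concerns what is recorded. A symptom that begins after the Month 3 visit cannot have been open at that visit. The stated purpose of the 28-day call does not reach it. A coordinator who follows the text could discuss only open events, or could treat the call as unnecessary for a patient who has none. What is at stake is the comfort of a small number of patients and the completeness of adverse event capture in the four weeks after treatment.

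**Working it through.** The plan states no figure to reproduce, so the check is mainly a comparison of the text, with a little arithmetic for the remedy.

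**1. Where adverse events are asked about.** The schedule in section C lists adverse events at Month 1, Month 2 and Month 3. That is 3 contacts up to the end of treatment. In the 28 days after Month 3 there is 1 contact, and 0 contacts at which a question about new events is stated.

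**2. Whether the exit text distinguishes the drugs.** It does not. The same words apply to pregabalin, for which section B describes effects of sudden stopping, and to the other three drugs, for which the protocol describes none.

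**3. What a step-down would involve.** The escalation schedule in section C begins "Pregabalin: 100 mg at bedtime for 1 week, then 100 mg 2 times a day for 1 week" and then moves to 100 mg three times a day. Reversing those steps from 300 mg/day gives:

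- Week 1: 100 mg twice a day, 7 × 2 = 14 capsules of 100 mg
- Week 2: 100 mg at bedtime, 7 × 1 = 7 capsules
- Total: 14 + 7 = 21 capsules over 14 days

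If the step-down starts at the Month 3 visit and the call comes 28 days after that visit, 28 − 14 = 14 days remain between the last dose and the call. The call would therefore cover both the step-down and the two weeks after it.

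**4. Whether extra supply is needed.** The three-month prescription is given at baseline without a stated quantity. Assume it is written at three 100 mg capsules a day throughout.

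- 84 days: prescribed 84 × 3 = 252; used 7 × 1 + 7 × 2 + 70 × 3 = 231; left over 252 − 231 = 21
- 90 days: prescribed 90 × 3 = 270; used 7 × 1 + 7 × 2 + 76 × 3 = 249; left over 270 − 249 = 21

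Under that assumption the escalation weeks leave exactly the 21 capsules required. If the prescription followed the escalation schedule instead, up to 21 more would have to be prescribed.

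**5. Number of calls.** The maximum enrolment is 400. Table 6 gives mean totals of 266 to 393 patients across its four scenarios. If every patient is already called at 28 days, the number of extra calls is zero and only the questions change.

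**The case against.** The strongest reply is that nothing is forbidden. Text saying a taper is not required leaves the decision with the physician, Month 3 must be an in-person visit, and the patient may simply continue the drug. Section E says the study was meant to resemble ordinary practice. Section B calls the effects low in frequency. All of this stands. It limits the point to a missing prompt and keeps it minor, but it does not explain why the exit text should steer sites away from a taper for the one drug with a described stopping effect.

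A second reply is that the coordinator would hear of new events anyway, or that the Safety Committee described in section E would act in real time. The first may be true, but the text does not ask for it. The committee can review only what someone reports.

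A third is that the drug-specific consent forms (Protection of Human Subjects) and Appendix B, Adverse Event, may already deal with both matters. Neither was available for this review, so that is possible. They would not change what the Month 3 and 28-day lines tell sites to do.

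It is also tempting to say that the protocol contradicts itself, since it allows stepping down elsewhere. That contrast is weak. At entry, "Screening/baseline period may take up to 14 days if patients need to titrate down off of medication" serves the washout of earlier drugs, and inclusion criterion 4 asks for at least 7 days off them. If those days fall inside the window, only about 14 − 7 = 7 remain for tapering. The dose reduction for intolerance in section C leads to a lower maintenance dose and is not a stopping taper.

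**Conclusion.** The point holds as a minor, inexpensive improvement in patient safety and adverse event capture. Followed literally, the text gives no prompt to step down pregabalin and schedules no question about events that begin after Month 3.

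Its size cannot be expressed as a number of events: section B gives no rate, and the plan does not say how many patients stop at Month 3. A reader might try to size it by multiplying the Table 5 quit rates by the Table 6 arm sizes. That counts simulated patients who stop before Month 3, not those who stop at it, so it does not measure this problem.

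Other stronger readings are not supported either:

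- **Endpoint or bias.** A reader might infer an effect on the efficacy or quit endpoints, or a bias between drugs. Both endpoints are fixed at 12 weeks, before any Month 3 stop, and the on-treatment side-effect comparison in Specific Aim 2 is complete by then.
- **Other drugs.** A reader might infer that all four drugs need a taper. The protocol describes effects of sudden stopping only for pregabalin.
- **Exclusion of new events.** The 28-day text does not bar recording new events; it only fails to ask for them.

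The conclusion assumes that the unseen Appendix B and consent forms do not already give these instructions.

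**What to change.** Make two wording changes in section C, b. Study Procedures.

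1. **28-day call.** Call every patient. Ask whether the assigned drug has been stopped and on what date, record any new adverse event since the Month 3 visit, and close open events. List post-treatment events by drug, separately from on-treatment events.
2. **Month 3 heading and item 8.** State that titration down is at the physician's discretion. For patients who stop pregabalin at Month 3, offer a step-down, for example 100 mg twice a day for 1 week, then 100 mg at bedtime for 1 week.

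The step-down should start after the Month 3 assessments are complete. The 12-week efficacy and quit endpoints and the quit definition under Missing data in section D then stay as they are. A patient who completes 12 weeks and then stops is not a quit. The change should not extend to stops before Month 3 and should not add a rule for dating a quit, because either would touch a primary endpoint.

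The cost is up to 400 short calls (fewer if all patients are already called), a little data entry, and up to 21 capsules per patient stopping pregabalin. The patient or insurer would pay for the capsules, since the study does not supply drug. If Appendix B or the drug-specific consent forms already cover these points, align the Month 3 and 28-day text with them.

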9. SF-12
10. 28 day post call.
  1. There will be a call by the study coordinator to close out any adverse events left open at the end of the study.

### Choice of Study Design

We chose the Bayesian Adaptive Design with efficiency in mind. Using adaptive randomization (being able to change how we assign patients to the drugs during the study based on information gained during the study) not only allows for substantially smaller sample sizes, but also provides better conclusions about what treatments are the most effective because it lets us make changes to our approach or stop the study early if we find strong results before the scheduled end of the study. We conducted extensive trial simulations comparing different designs measuring the resources (time and number of patients required) and the ability to draw important conclusions about relative efficacy of the four drugs (i.e., which is better) and selected the proposed design as the most effective and efficient.

### Choice of Outcomes

Patients will complete a Likert-type scale for pain, the PROMIS 6 item pain interference scale, the SF-12, and the PROMIS fatigue and sleep disturbance scales. The first endpoint, or outcome, is a patient responder-defined measure of efficacy (i.e., if the patient reports a pain score at the end of 12 weeks that is 50% or greater from what they reported when they started the study, then it is efficacious for that patient). The second endpoint is the percentage of patients who discontinue treatment. Our secondary endpoints, SF-12, pain interference, fatigue, and sleep disturbance, also will be longitudinally modeled (see content after Table 5.)

## **D. Analytic Methods**

### Overview

The primary aim of this study is to determine which drug is most effective and most tolerable in producing pain relief. We will perform a prospective randomized comparative effectiveness adaptive design study with those who do not have diabetes and in whom no other cause for neuropathy has been found. We have an agreement from 40 sites to participate in the study and four drugs will be tested. In this design we will perform several interim analyses (interims) while controlling the overall Type I error rate.

The following sections focus on specific details of this design and detail how we determined power, sample size, and duration of this trial. Throughout we add information to help those less familiar with our design and analyses better understand what we did and plan to do with this study.

### Bayesian Adaptive Design

Patients will be randomized to one of four treatment arms (groups) with a maximum number of patients  $n_{max}=400$ . Using a Bayesian Adaptive Design, at each interim analysis a decision will be made to either continue enrolling patients or to stop the trial for success. If patient enrollment continues, the randomization structure (i.e., how we randomize patients to each drug) will also be updated. Two endpoints are used to drive the adaptive randomization and stopping criteria. The first endpoint is the percentage of patients who report a 50% or greater decrease on the Likert-type pain scale after 12 weeks. The second endpoint is the percentage of patients that discontinue treatment. After 80 patients are enrolled (see definition of “enrolled” in the consent form section towards the end of this protocol) and equally randomized to the four arms, we begin adapting the randomization. Then, after we have endpoint data on 100 patients, the data will be analyzed (a first interim analysis) and an updated randomization schedule will be used. Specifically, the arm, or drug, that looks to be the best

will get more participants allocated to it in this subsequent randomization. A new adaptive randomization schedule will be updated and an interim analysis will occur every 13 weeks after the first interim analysis, using up to date outcome data, until the trial is stopped (i.e. for early success). Early success stopping criteria will be if the probability of the maximum arm (i.e., the best drug), measured by a combined utility of the pain and treatment discontinuation endpoints, is larger than 0.925. While this will halt new patient enrollment, we will confirm this finding with a subsequent analysis and evaluation after all data from all enrolled patients are obtained as some will still be actively in the study when the early stopping criterion is identified. Also determined is which of the arms are losers, and is defined as an arm that has a probability of being maximum as less than 0.01. This will be a useful result in cases where a best arm could not be identified. If a loser or two is identified then the drug(s) would not be recommended for use in clinical practice.

A summary of the overall general design is as follows.

- Begin a new adaptive randomization schedule once 20 patients have been enrolled on each treatment.
- Stop for success if the probability a treatment is best, defined as  $pr(t_i \text{ is best}) > .925$ , for some treatment.
- Perform an interim analysis after 100 patients have 12 week data and every 13 weeks thereafter.
- For interim analyses, all data are used on all enrolled patients with at least 4 weeks of data.
- For the final analysis: (1) a treatment is best if  $pr(t_i \text{ is best}) > .925$  or (2) a treatment is loser if  $pr(t_i \text{ is best}) < .01$ .

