### Statistical Model

Of necessity the following is fairly technical, but it is needed to allow for appropriate statistical review and because it is the statistical model that will evaluate final determination of which drug is "best". This is referred to as the arm of maximum utility (i.e., the drug with the

best combination of patient reported efficacy and percentage of patients who quit taking the drug.) For this study the two endpoints are respectively  $S_{EjT}$  for efficacy and  $S_{QjT}$  for quitting. The number who did not quit and were not efficacious is  $Sn_{EjT}$ . These are modeled as a multinomial distribution  $(S_{QjT}, S_{EjT}, Sn_{EjT}) \sim \text{MultNomial}(\theta_j^q, \theta_j^e, \theta_j^{ne})$ . In addition, we provide “weakly informative” priors,  $(\theta_j^q, \theta_j^e, \theta_j^{ne}) \sim \text{MultNomial}(1/3, 1/3, 1/3)$ . Using the endpoint data and the prior probabilities, we then use Markov Chain Monte Carlo computations to obtain the Bayesian posterior distributions of  $\{\theta_j^e | S_{EjT}\}$  and  $\{\theta_j^q | S_{QjT}\}$  respectively for each endpoint (i.e., efficacy and quitting.)

The utility function previously discussed is used for determining whether we have met our stopping criterion. Specifically, the rule is we will stop the trial if the probability of an arm (i.e., a drug) having maximum utility is greater than 0.925. This may first be determined after enrolling 100 of the 400 potential patients. The utility function is

$$U_{jT} = .75\{\theta_j^e | S_{EjT}\} + 1 - \{\theta_j^q | S_{QjT}\} \text{ and the arm (or drug) having the maximum utility is}$$

$U_{\max,T} = \max(U_{1T}, U_{2T}, U_{3T}, U_{4T}, U_{5T})$ . The stopping rule is mathematically  $P(U_{\max,T}) > .925$ . If a maximum utility arm (drug) is not identified after completed data on 100 patients, this procedure and accrual will continue until a maximum arm is identified or we reach 400 enrolled patients. At the end of the trial we will also decide that an arm is a “loser” if there is a very unlikely chance that it is the best,  $P(U_{\max,T}) < .01$ .

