### Power, Sample Size, and Trial Duration

We performed several trial simulations based on the various combinations of efficacy (5 types) and quit (3 types) endpoints that were shown in Table 4. We varied the maximal accrual into the study after several weeks and, as previously identified, found 4.2 patients/week to be very close to the optimal combination of sample size and trial duration. These simulations resulted in identifying power (the probability of success) in two components—one for early success (i.e., being able to stop the trial early) and one for late success of the trial (i.e., after enrolling all 400 patients) (see Table 5). While some of these combinations are very unlikely to occur, we include all possible combinations in Table 5, ordered from most to least power. We highlight four scenarios, here.

**First** we want to highlight the unlikely scenario that serves as our null hypothesis (**scenario #1 in Table 6**). In this scenario there are no differences in efficacy or in quit rates among the drugs. Therefore, the extent to which this scenario is "successful" actually reflects our Type I error rate. For this scenario, we estimated (identified) that 5.5% of the simulated trials had early success, .6% late success. Thus this trial scenario produced an appropriate expected Type I error ( $\alpha \sim .05$ ). The sample size of this scenario on average was 393 patients. The average length of the trials under this scenario was 108 weeks. **Second (scenario #2 in**

**Table 6)**, if there is a best drug and second best drug in terms of efficacy and quit rates, we estimated (identified) that 78% of the simulated trials had early success, 2% had late success, and 20% had incomplete results. This trial scenario had 80% power and the sample size of this trial scenario was on average 298. The average length of this trial scenario was 78 weeks.

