**Third (scenario #3 in Table 6)**, if there is one strong best drug in terms of efficacy and quit rates, we estimated (identified) that 92% of the simulated trials had early success, 2% late success, and only 6% had incomplete results. Thus this simulation had 94% power. The average sample size of this trial scenario was 266. The average length of these simulated trials was 68 weeks. Close to half of the sample size, 108, was on the best treatment. **Fourth (scenario #4 in Table 6), a very unlikely case, is** if there is one strong best drug in terms of efficacy and but quit rates that are higher for the drug with high efficacy, we estimated (identified) that 10% of the simulated trials had early success, 2% late success, and 88% had incomplete results. Thus this simulation had 12% power. The average sample size of this trial scenario was 387. The average length of these simulated trials was 107 weeks. However, this trial does a decent job correctly identifying treatment 2 as the loser (65%).

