**Table 5. Simulation scenarios.**

		Treatment			
		1	2	3	4
Scenario 1	Pr(Quit)	0.2	0.2	0.2	0.2
Eff: No Difference	Pr(Efficacy)	0.3	0.3	0.3	0.3
Quit: No Difference	Utility	1.025	1.025	1.025	1.025
Scenario 2	Pr(Quit)	0.3	0.25	0.15	0.3
Eff: Best and 2 nd Best	Pr(Efficacy)	0.3	0.4	0.5	0.3
Quit: Positive	Utility	0.925	1.050	1.225	0.925
Scenario 3	Pr(Quit)	0.3	0.25	0.15	0.3
Eff: One Strong Best	Pr(Efficacy)	0.3	0.3	0.5	0.3
Quit: Positive	Utility	0.925	0.975	1.225	0.925
Scenario 4	Pr(Quit)	0.2	0.4	0.4	0.2
Eff: One Strong Best	Pr(Efficacy)	0.3	0.3	0.5	0.3
Quit: Negative	Utility	1.025	0.825	0.975	1.025

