**Table 6. Simulated Trial Operating Characteristics.**

Scenario	Prob. Success	Prob. Early Success	Mean Trial Weeks	Mean Patients				
				Total	T1	T2	T3	T4
1 (No Difference)	0.061	0.055	108	393	99	99	97	99
2 (Best & 2nd Best+)	0.798	0.777	78	298	51	80	116	52
3 (One Strong Best+)	0.939	0.923	68	266	51	58	105	51
4 (One Strong Best-)	0.115	0.103	107	387	108	62	107	109

Prob. Drug Wins

Prob. Drug

Scenario	Pr(Treatj Best)>.925				Loses Pr(Treatj Best<.01)			
	T1	T2	T3	T4	T1	T2	T3	T4
1 (No Difference)	0.015	0.015	0.014	0.017	0.075	0.064	0.088	0.068
2 (Best & 2nd Best+)	0.000	0.001	0.797	0.000	0.744	0.238	0.000	0.736
3 (One Strong Best+)	0.000	0.000	0.939	0.000	0.661	0.461	0.000	0.682
4 (One Strong Best-)	0.053	0.000	0.011	0.051	0.030	0.647	0.104	0.034

NOTE: For Quit, "positive" means quit percentages are low and "negative" means quit percentages are high

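### The plan turns an unlikely-to-be-best label into advice against a drug without a trial-level error rate; under its own null that rate is 8.8% to 29.5%, about 23–25% by simulation

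*Combined protocol and SAP*

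**What the plan says.** The Bayesian Adaptive Design section sets a cut-off of 0.01 for the label: "Also determined is which of the arms are losers, and is defined as an arm that has a probability of being maximum as less than" that value. It adds "This will be a useful result in cases where a best arm could not be identified" and then gives the consequence: "If a loser or two is identified then the drug(s) would not be recommended for use in clinical practice". That consequence is not limited to trials without a best arm. The Statistical Model section is narrower: at the end of the trial an arm is a loser if "there is a very unlikely chance that it is the best".

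On error rates, the Overview promises control of the overall Type I error across the interim analyses. The Power, Sample Size, and Trial Duration section takes the scenario with no differences as the null and says that the extent of success there "actually reflects our Type I error rate": 5.5% early plus 0.6% late. Success means declaring a best drug. Table 6 prints loser rates for each arm separately. The only one the text discusses is the correct call of treatment 2 (T2) in Scenario 4, at 65%.

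**The concern.** The conclusion goes further than the evidence. A posterior probability of being best below 0.01 ranks a drug against three active comparators. With no placebo group, the trial cannot show that a loser does not work. A close second can earn the label when the leader is clearly ahead, and one of several equal drugs can earn it by chance.

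The conclusion also has no error rate at the level at which it is drawn. Advice against a drug follows if any arm is labelled, so the relevant figure is the probability of at least one false loser in the trial. The plan does not report it.

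The advice could have effects. The background sections say that insurers already refuse some prescriptions for these patients, and a published statement that a drug is not recommended could be used in the same way.

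**Working it through.** **1. Reproducing the plan's null figures.** Inputs: efficacy 0.30 and quit rate 0.20 in every arm (Tables 4 and 5), and U = 0.75E + 1 − Q. Every arm then has U = 0.75 × 0.30 + 1 − 0.20 = 1.025, so any loser is a false one. Table 6 success is 0.055 + 0.006 = 0.061, which equals the sum of the four winner columns: 0.015 + 0.015 + 0.014 + 0.017 = 0.061.

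**2. Bounds from Table 6 alone.** The null loser rates are 0.075, 0.064, 0.088 and 0.068.

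- Lower bound for at least one loser: the largest single rate, 0.088.
- Upper bound: the sum, 0.075 + 0.064 + 0.088 + 0.068 = 0.295.
- If the arms were independent: 1 − 0.925 × 0.936 × 0.912 × 0.932 = 0.264.
- A tighter floor holds if winner and loser are read from the same final posterior. At most three arms can be losers, and three losers leave the fourth above 0.97, which makes it a winner. So P(any) ≥ (0.295 − 0.061)/2 = 0.117. By the same reasoning, P(any loser and no winner) ≥ (0.295 − 3 × 0.061)/2 = 0.056.

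**3. Re-simulation of the null.** Settings from the plan: 80 patients randomized equally, allocation by the plan's formula, first look at 100 patients with 12-week data, imputation by the longitudinal model, maximum 400. Assumptions: the prior is read as Dirichlet(1/3, 1/3, 1/3) and accrual ramps up over 8 weeks to 4.2 per week.

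| Run | Trials | At least one loser | At least one loser and no winner |
|---|---|---|---|
| Adaptive, 13-week looks | 4,000 | 23.2% | 21.0% (final analysis); 19.9% (neither early nor late success) |
| Adaptive, 13-week looks | 2,000 | 22.7% | 20.8% |
| Adaptive, 13-week looks | 2,000 | 22.6% | 19.8% (final); 18.3% (neither early nor late) |
| Adaptive, 13-week looks | 1,500 | 23.6% | 20.8–21.7% (both definitions) |
| Adaptive, 4-week looks | 1,000 | 24.0% | 21.7% |
| Equal allocation, 13-week looks | 4,000 | 25.6% | 22.0% (final); 20.4% (neither) |
| Fixed 99 per arm, no interims | 6,000 | 23.9% | not tabulated |

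The standard error for 22.7% in 2,000 trials is √(0.2265 × 0.7735/2000) = 0.9 points.

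**4. How well the re-simulation matches Table 6.** The 4,000-trial adaptive run gave success 0.043 against 0.061, mean sample size 394 against 393, and per-arm losers 0.062–0.066 against 0.064–0.088. With equal allocation, success was 0.062 and losers were 0.069–0.078. For other scenarios (1,500 trials each), success was 0.790 against 0.798 (Scenario 2), 0.940 against 0.939 (Scenario 3) and 0.108 against 0.115 (Scenario 4). The adaptive runs name slightly fewer null losers per arm than Table 6, so they are unlikely to overstate the overall loser rate.

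**5. Outside the null.** In Scenario 4, T1 and T4 are joint best: U = 1.025 each, against 0.825 for T2 and 0.975 for T3 (Table 5). Table 6 still names them losers in 0.030 and 0.034 of trials. The chance that at least one is named is therefore between 0.034 and 0.030 + 0.034 = 0.064. Re-simulation (1,500 trials) gave 0.051, of which 0.030 with no winner.

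Scenario 2 is an illustration only. T2 is second best (U = 0.75 × 0.40 + 1 − 0.25 = 1.050, against 0.925 for T1 and T4 and 1.225 for T3), yet Table 6 labels it a loser in 23.8% of trials. That label is correct as not best. In re-simulation it nearly always came with a declared winner: 0.305 of 0.316, leaving 0.011 without one. That run overstates Table 6's 0.238.

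**The case against.** The strongest reply is that nothing is hidden. Table 6 prints all four null loser rates and those for Scenario 4, and the Statistical Model section gives the label its correct meaning. In a comparative trial, not recommended may simply mean not the drug to choose among these four. The plan calls the null unlikely and Scenario 4 very unlikely. If all four drugs are equal, advising against one costs nothing in average utility. A familywise rate for a Bayesian label is also partly a matter of preference.

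Much of this is fair, and it limits the point to wording and reporting. But the advice sentence carries no qualifier that would confine it to a choice among the four. The plan already uses the unlikely null to justify its winner error rate, so the same null should be reported for its other declared conclusion. From the printed rates a reader can only bound the any-loser rate, and the range is wide. Equal average utility does not remove the effect on access to the drug that was named.

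The no-winner rate is the softest figure. Most of it rests on simulation, the runs give fewer null winners than Table 6 (as low as about 0.02 when only the final analysis counts), and it moves with the definition of a winner. Table 6 by itself supports only a floor of 5.6%.

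**Conclusion.** The concern holds. The loser rule supports the statement that a drug is unlikely to be the best of four, and the plan goes on to advise against its use with no stated trial-level error. Under the plan's null the chance of at least one false loser is certain only to lie between 8.8% and 29.5%. Re-simulation puts it at 22.6–24.0% with adaptive allocation and 25.6% with equal allocation, roughly four times the 6.1% that the plan reports for a false winner (0.232/0.061 = 3.8). Trials with a false loser and no winner make up about one in five (18–22% across runs and winner definitions). In Scenario 4 a joint best drug is named a loser in 3.4–6.4% of trials. The bounds need only Table 6; the point values rest on the reading of the prior, the accrual ramp and the timing of looks. This should be fixed, but it does not threaten the winner analysis.

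**What to change.** 1. Replace the advice sentence in the Bayesian Adaptive Design section with: a loser is a drug unlikely to be the best of the four; this alone does not support a recommendation against its use.
2. From the existing simulations, tabulate the probability of at least one loser under Scenario 1, both overall and jointly with no declared winner. State whether a winner means early or late success, or the final analysis only. Put these figures beside the winner error rate in the Power, Sample Size, and Trial Duration section and in Table 6.

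The cost is one sentence and one tabulated rate, with a weaker negative conclusion as the only loss. The 0.01 cut-off, allocation, stopping rule, sample size and winner analysis stay as they are.
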